#Assessment via telephone or in person

@ Pregnancy test to be performed no greater than 14 days prior to consent in study.

If patients are unable return to the clinic for any of the scheduled assessment days (Day 15, Day 29, Day 36, and/or Day 57), we will contact the patient via telephone to complete the symptom and quality of life assessments (ESAS, HADS, FACT-G, FACIT-F, and GSE). If contacted by phone, then physical assessments will not be performed.

Adverse events will be captured according to the recommended AE recording guidelines for a Phase II protocol.

C.7. Symptom Assessment

C.7.1. Demographic variables

Demographic variables will include patient self-reported birth date, sex, marital status, ethnicity, education, and job status, primary cancer, cancer treatment within the last year, surgery, chemotherapy, immunotherapy or radiotherapy, and medications including opioid dosage. **(APPENDIX P).** Appendix P also includes tracking the baseline labs ordered and an off study note that will be completed once the patient has been taken off study.

C.7.2.Symptom assessment (see Table 3)

The Functional Assessment of Chronic Illness Therapy-Fatigue (FACIT-F) (including the Functional Assessment of Chronic Illness-General (FACT-G) and Fatigue subscales), Hospital Anxiety and Depression Inventory (HADS), Edmonton Symptom Assessment System (ESAS), Symptom Digit Modalities Test (SDMT) and Six minute walk test, will be used assess outcomes.

Adherence: Patients with similar characteristics to those of patients we will admit to the study have demonstrated strong adherence to assessments of the same duration in studies conducted by our group [128,129,137,138]. These assessment tools have been validated and are reliable for use in the collection and analysis of data. Also patients in this study with not undertake time intensive radiological tests such as MRI'S or drug pharmacokinetic studies which are a common part of clinical trials. This would enable help in completion and minimize attrition.

C.7.2.1. Outcome Measures

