We hypothesize that patients randomized to receive P. ginseng will demonstrate greater improvement in depression, anxiety, and overall symptom burden, as compared to placebo. In order to achieve these secondary aims we will assess depression and anxiety using HADS, overall symptom burden using ESAS, Physical activity by Hand grip strength and hand grip endurance test, and quality of life using FACT-G.. Depression and Anxiety. Depression and anxiety symptoms will be assessed using the 14-item HADS [147] questionnaire. This questionnaire asks patients to underline the statement that most closely matches how they have been feeling in the previous week. This questionnaire has been found to be valid and reliable in a number of clinical situations and has been widely used in medically ill patients. Other Common Symptoms. The ESAS [135,136] measures 10 common symptoms in the past 24 hours (pain, fatigue, nausea, depression, anxiety, drowsiness, shortness of breath, appetite, sleep, and feeling of well-being) during the previous 24 hours; This questionnaire has been found to valid and reliable in cancer populations. Neurocognitive function will be measured using the Symbol Digits Modalities Test

(SDMT). This is a useful diagnostic tool measuring clerical speed, visual search and memory, fine motor control and concentration. (Turner M. Symbol Digit Modalities Test. Staines: Dyslexia Institute. 1999.) **Physical Activity:** a) The Six-Minute walk test will be used to assess physical function and has been recommended by the American Thoracic Society (ATS) as an objective measure of functional capacity [148]. This test has been found to be an objective measure of functional capacity in patients with chronic respiratory conditions, fibromyalgia, stroke, and cancer. Our group has used this methodology in the assessment of fatigue and dyspnea. Our previous study demonstrated that 6-minute walk in patients with fatigue and dyspnea related to lung cancer was well tolerated. All 33 (100%) patients were able to tolerate two episodes of 6-minute walks within half hour [149]. Assessment will occur at baseline, day 29 and Day 57.

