Hand Grip Strength and Endurance Test: The hand grip strength and endurance test will be administered at baseline, Day 15, 29, and 57. The purpose of this test is to measure the maximum isometric strength of the hand and forearm muscles. The patient will hold the dynamometer in the hand to be tested, with the arm at a right angle and the elbow by the side of the body. The handle of the dynamometer is adjusted if required - the base should rest on the first metacarpal (heel of palm), while the handle should rest on the middle of four fingers. When ready, the patient squeezes the dynamometer with maximum isometric effort, which is maintained for about 5 seconds. No other body movement is allowed. The patient will be strongly encouraged to give a maximum effort.

Blood will be collected from consenting patients (optional procedures) for future investigational studies to explore ginseng's effect on induced monocyte inflammatory cytokines (IL-1 β , IL-6, IL-10 and TNF- α) production and the serum levels of these cytokines (IL-1 β , IL-6, IL-10 and TNF- α) in cancer patients. The blood samples will be stored in a -80°C freezer for future studies on cytokine levels in patients with cancer and cancer-related fatigue[152]. Optional procedure lab draws will be documented in a sample log that will include the data of blood draw, signature of person obtaining blood sample as well as the storage conditions and location (-80 degree freezer in laboratory of [name]).

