We will summarize patient characteristics of all patients enrolled in the pilot study. Means and standard deviation or medians and IQRs will be calculated. We will also perform exploratory analyses on the changes in FACIT-F subscale (primary outcome measure) from baseline to Day 29 and baseline to Day 57. Similar analysis will be conducted for the secondary outcomes (FACT-G, ESAS symptoms, HADS, SDMT, six- minute walk test, Borg Scale, GSE and Hand Grip Strength and Endurance Test). Based on whether the data is normally distributed (Shapiro-Wilk test) we will use paired t-tests or Wilcoxon Ranked Sum tests. We will also summarize fatigue scores, other secondary outcomes at each point in time and the frequency and type of side effects as determined by NCI CTCAE V4 criteria.

Safety Monitoring

Safety Monitoring

Because this Panax ginseng has not been previously evaluated in cancer related fatigue, we will implement this study in two phases and we will utilize early stopping rules for dose-limiting toxicities (DLTs) for 30 patients in the treatment arm (Arm 2, Panax ginseng 800mg/day) before the main phase of the study begins. A DLT is defined as any Grade 3 or 4 toxicity that is attributable to the treatment regimen.

In the first phase, we will enroll up to 30 evaluable patients in the Arm 2 (treatment arm); patients will not be enrolled in the placebo arm. Recruitment for the main study will be delayed until these original 30 patients are evaluated for DLTs. We will base early stopping rules on a method proposed by Thall et al., (160) and using the Multc99 software from the Department of Biostatistics.

To ensure that the true DLT rate is sufficiently low, we will terminate the study early if the probability that the estimated toxicity rate is greater than 10% (given the results) is greater than 0.95. We assume a prior of Beta (0.1,0.9) in these calculations. The study will be stopped early if (# patients with DLT) / (# patients evaluated) >= 3/6, 4/10, 5/16, 6/22, or 7/29.

The table below shows operating characteristics given differing true toxicity rates based on 10000 simulations for each row:

	Probability	Achieved Sample Size		
True DLT rate	Early Stopping	25 th , 50 th , 75 th percentiles		
1%	<0.0001	30	30	30

Operating Characteristics for first phase early stopping rule (based on DLT)

3%	0.002	30	30	30
5%	0.013	30	30	30
8%	0.053	30	30	30
10%	0.116	30	30	30
15%	0.324	20	30	30
20%	0.597	9	21	30
25%	0.791	8	14	27
30%	0.917	6	9	17
40%	0.993	6	7	9

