Secondary Analyses: We will compare the physical activity levels of participants in the two groups as measured by the hand grip dynamometer. We will also test the quality of life variables with the HADS and FACT-G tests. As each of these variables is also continuous and measured at the same points in time, we will determine the relationship of each of these variables to fatigue and analyze the data using repeated measures analyses as described above, testing for differences between groups, over time, and a time by group interaction. If several variables appear to be significantly related to fatigue, we will also perform multivariate analyses to determine the best predictors of fatigue as measured by the FACIT-F subscale. We will also determine relationships between daily or weekly fatigue, symptom data, and daily measures of sleep duration and fragmentation by determining correlation coefficients within time periods. Exploratory analyses of all subscale scores will be performed after the primary endpoint has been analyzed.

Summary information on the global symptom evaluation by group will also be provided at each of the assessed time points. Differences in distributions between groups will be analyzed using a chi-square analysis.

On an exploratory basis, we will also investigate whether or not different results were found for patients with different types of cancer, primarily using descriptive statistics. We do not expect to find statistical significance due to the low numbers of patients in each cancer type, but if we do find trends that appear to be significant, we will use this information to inform a future study. Additionally as a part of exploratory analysis, we will use Pearson chi-squared tests to compare the proportion of patients experiencing clinical benefit between each arm.

Information about toxic effects and tolerability will be summarized at each dose level. Safety assessments including hematology and chemistry assessments and toxicity evaluations will be made throughout the study (see Table 3).

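### Grip, six-minute walk and SDMT go unmeasured at telephone visits and no missing-data method covers them, so estimates of change over time may lean toward improvement if worsening patients stay away

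*Combined protocol and SAP*

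**What the plan says.** Table 3 schedules grip, six-minute walk and SDMT at baseline and Days 15, 29 and 57. Section C.7.2.1 agrees for grip ("The hand grip strength and endurance test will be administered at baseline, Day 15, 29, and 57") but leaves Day 15 out for the walk test ("Assessment will occur at baseline, day 29 and Day 57").

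The notes to Table 3 set out the telephone fallback. Its trigger is "If patients are unable return to the clinic for any of the scheduled assessment days", and then "we will contact the patient via telephone to complete the symptom and quality of life assessments (ESAS, HADS, FACT-G, FACIT-F, and GSE"). The next sentence is "If contacted by phone, then physical assessments will not be performed". SDMT is not a questionnaire on that list, so by omission it too is missing at a telephone visit.

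Two parts of section C.9 analyse these outcomes over time:

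- **Pilot Analysis** (single-arm Phase I) examines change from baseline to Day 29 and to Day 57 in the secondary outcomes, including walk, grip and SDMT: "we will use paired t-tests or Wilcoxon Ranked Sum tests". It also summarises each outcome at each visit.
- **Secondary Analyses** (Phase II) names grip, HADS and FACT-G. It says "As each of these variables is also continuous and measured at the same points in time", and plans repeated measures "testing for differences between groups, over time, and a time by group interaction". Walk and SDMT are not named there.

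The one missing-data rule, last value carried forward in a secondary analysis, is given under Power Considerations and applies to FACIT-F alone.

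**The concern.** For grip, the premise that the secondary variables share the same measurement times fails at every telephone visit. HADS and FACT-G are collected by telephone and grip is not. After baseline, grip, walk and SDMT values come only from patients who attend.

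Non-attendance could well be related to health. The eligibility criteria require fatigue of at least 4 out of 10, allow Zubrod up to 2 and admit patients on chemotherapy or radiation. Section B.5 expects a longer study to lose patients to complications and death. If patients who get worse stay away, those still measured will show a better average change than the whole group. The pilot has no placebo arm to absorb that shift.

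The planned analysis also makes no use of useful information: patients without a grip, walk or SDMT value will usually have a FACIT-F and an ESAS from the same telephone contact. The stakes are modest, since these are exploratory objectives, but section D.10 intends the secondary trends to support larger trials and grant applications.

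**Working it through.** **The plan's own figure.** The documents give no variance, effect size or telephone share for grip, walk or SDMT. The only related figure is for FACIT-F: (1.96 + 0.84) × 5.8 × √(2/50) = 3.25, stated as 3.3. It reproduces, and is used below only as a standardised fatigue effect: 3.3 / 5.8 = 0.57 SD.

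**Assumptions, none from the documents.** Let *f* be fatigue change (higher is better) and *w* function change, each with SD 1, true mean change zero and correlation ρ = 0.3 or 0.5. The telephone share is 20%, 30% or 40%. The probability of return is logistic in *f* with slope 1 or 1.5, so the odds of return multiply by e^1 = 2.7 or e^1.5 = 4.5 per SD.

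**Within-patient change among returners.** If return depends only on *f*, then mean *w* among returners = ρ × mean *f* among returners. Simulation (at least 400,000 patients per scenario) gives mean *f* among returners from 0.18 (20% telephone, slope 1) to 0.43 (40%, slope 1.5):

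- Low end: 0.3 × 0.18 = 0.05 SD.
- High end: 0.5 × 0.43 = 0.21 SD.
- At ρ = 0.5 and 30% telephone: 0.13 to 0.16 SD.
- Return unrelated to health: 0.00 SD in every scenario.

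**Meaning for the pilot.** With 30 patients, 20-40% telephone visits and no other loss, 24 to 18 are measured. For a paired t-test with n patients and bias δ (SD taken as 1), the noncentrality is δ√n. For n = 24, δ = 0.05 it is 0.24, and two-sided 5% rejection becomes 5.6%. For n = 18, δ = 0.21 it is 0.89, and rejection becomes 13.4%.

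**Dependence on the reason for non-return.** A second simulation used a standardised outcome, true change zero, baseline to follow-up correlation 0.8 and 20% not returning. Apparent change in SD:

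| Return depends on | Paired change | Likelihood repeated measures, all baselines kept |
|---|---|---|
| nothing relevant | 0.00 | 0.00 |
| baseline fitness | -0.05 | 0.00 |
| current fitness | +0.05 | +0.10 |
| the patient's own change | +0.16 | +0.15 |

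Keeping all baselines is therefore not sufficient when return follows the patient's own course.

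**Between arms.** With the same return mechanism in both arms and no treatment effect, the bias is 0.00. If ginseng eases fatigue by 0.57 SD and does nothing to function, more ginseng patients return and they are less selected. The contrast is then biased against ginseng by 0.02-0.07 SD. With 30% telephone visits, 50 × 0.7 = 35 per arm are measured and the standard error is √(2/35) = 0.24 SD. Rejection moves from 5% to at most about 5.9%.

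**Does the same-visit fatigue score repair it?** Bias left after regression imputation from *f*, with the same ρ, slopes and shares:

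- Return depends on fatigue only: 0.00 SD. This is guaranteed by the assumption.
- Return depends equally on fatigue and function: 0.08-0.29 SD.
- Return depends on function only: 0.13-0.40 SD, against 0.17-0.43 SD before imputation.

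**The case against.** A reader might infer that the planned tests set all patients at baseline against a fitter subset later, and so show improvement by construction. The documents do not support that. Paired t-tests use the same patients at both times, and repeated measures works within patient. Only the pilot's visit-by-visit summaries mix the two populations, or a literal unpaired rank-sum test; the latter is offered as the alternative to a paired test, so signed-rank is probably meant. Nor is the direction fixed: bias is zero if return is unrelated to health, and slightly negative for a paired test if return depends on baseline fitness.

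A reader might also take telephone patients to be the sicker ones. The text says only that they are unable to return. Section C.6.2 lets patients have laboratory tests at an outside facility, so distance and logistics fit equally well. This objection stands: informative missingness is plausible here, not shown.

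The Phase II question is the randomised contrast, where the bias is small, and of the outcomes in Secondary Analyses only grip is affected. That also stands, and it is why the pilot carries most of the concern. What the objection does not answer is that the plan states no handling for outcomes it knows will be absent at telephone visits.

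**Conclusion.** The point holds as a modest improvement to the analysis plan. Follow-up grip, walk and SDMT rest on clinic returners, with no stated missing-data method, and change over time may be biased toward improvement if worsening patients stay away. The size is about 0.05-0.21 SD if return depends on fatigue change, and zero if it is unrelated to health. It rests wholly on the assumed correlation, telephone share and return slope. The uncontrolled pilot is the main exposure. Between-arm bias is about 0.02-0.07 SD against ginseng under an assumed 0.57 SD fatigue benefit, and zero under the null with equal missingness. It would be going too far to say that imputing from fatigue removes the problem: that is true only if return depends on fatigue and not on function itself.

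**What to change.** In both Pilot Analysis and Secondary Analyses:

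1. Analyse grip (both), and walk and SDMT (pilot), by multiple imputation or a joint mixed model that keeps every baseline and includes the same-visit FACIT-F and ESAS fatigue scores.
2. Correct the statement on common measurement times: grip has no value at a telephone visit. State explicitly whether SDMT is omitted by telephone.
3. Report the number measured by arm and visit, and show visit summaries of change in patients measured at both visits.
4. Add a missing-not-at-random sensitivity analysis that makes the imputed changes worse by a range of amounts. The bias left when return depends on function, divided by the telephone share, runs from 0.13 / 0.20 = 0.65 SD to 0.40 / 0.40 = 1.0 SD. A range from 0 to about 1 SD of change would cover those scenarios.
5. Name the signed-rank test if that is meant, and reconcile the Day 15 walk test between Table 3 and section C.7.2.1.

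Recording contact mode and reason for non-return would help in judging the assumption. The cost is SAP wording and a little more analysis, with no new patient assessments. The downside is a missing-at-random assumption given the fatigue scores, which item 4 tests.

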Global Symptom Evaluation. This instrument is to estimate the minimal important difference in symptoms before treatment and after treatment. Patients will be asked about their symptoms (worse, about the same, or better) after starting new medication. If their answer is better, patients will be asked to rate how much better their symptoms are (almost the same, hardly any better at all, a little better, somewhat better, moderately better, a good deal better, a great deal better, a very great deal better). If their answer is worse, patients will be asked to rate how much worse their symptoms are (almost the same, hardly worse, a good deal worse, a great deal worse, a very great deal worse, somewhat worse, moderately worse, a good deal worse, a great deal worse, a very great deal worse). This evaluation will be performed on day 29 and day 57. **Toxicity Evaluation.** On Day 29, the study will be completed and patients will be given the option of continuing on an open label basis, Panax ginseng 800 mg per day, will be provided they have tolerated the double-blind phase without moderate to severe toxicity as per NCI CTCAE V4 criteria. Toxicities will be evaluated using the NCI CTCAE Version 4 Criteria (Appendix A) on Days 8, 15, 21, 29, 36, 43 and 57 (all +/- 3 days). Adverse event (including event name, grade, start/stop date and attribution) will be documented in the medical record and entered into PDMS/CORe. PDMS/CORe will be used as the electronic case report form for this protocol.

The Investigator or physician designee is responsible for verifying and providing source documentation for all adverse events and assigning the attribution for each event for all subjects enrolled on the trial

C.8 Serious Adverse Events Reporting

An adverse event or suspected adverse reaction is considered "serious" if, in the view of either the investigator or the sponsor, it results in any of the following outcomes:

• Death

• A life-threatening adverse drug experience – any adverse experience that places the patient, in the view of the initial reporter, at immediate risk of death from the adverse experience as it occurred. It does not include an adverse experience that, had it occurred in a more severe form, might have caused death.

- Inpatient hospitalization or prolongation of existing hospitalization
- A persistent or significant incapacity or substantial disruption of the ability to conduct normal life functions.
- A congenital anomaly/birth defect.

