This is a preliminary study to explore the efficacy of P. ginseng in reducing fatigue as measured by the Functional Assessment of Cancer Therapy- Fatigue (FACIT-F) subscale. Because this Panax ginseng has not been previously evaluated in cancer related fatigue, we will implement this study in two phases. In the first phase(initial non dose escalating phase), we will enroll up to 30 patients in the Arm 2 (treatment arm); patients will not be enrolled in the placebo arm. Recruitment will be halted until these original 30 patients can be evaluated for DLTs. In the second, main phase patients will be randomized to receive either Panax ginseng or placebo. As a

2009-0854 January 21, 2016 Page 23 of 33

primary analysis, we will assess the level of fatigue at baseline and after 29 days to determine group differences in fatigue changes over time using analysis of variance. This analysis will test for differences between groups, differences over time, and a group by time interaction. We will also perform a repeated measures analysis by group using all available time points (for the FACIT-F fatigue subscale at baseline, day 15 and day 29). This analysis will test for differences between groups, differences over time, a group by time interaction, and trends over time. For all analyses of continuous variables, if the data are not approximately normally distributed, we will either use a nonparametric equivalent of the statistical test or we will transform the variable to achieve approximate normality. The design of the study is intent to treat, i.e., it is our aim to analyze anyone who received at least a single dose for both toxicity and response. Response would be considered clinical beneficial if they improve 3.5 points on the FACIT- F fatigue subscale at day 29 or day 15 (if day 29 is unavailable). Patient who have not completed at least day 15 would be considered inevaluable for consideration of clinical benefit.

Pilot Analysis:

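### The GSE's worsening scale is misprinted, the pilot plan tests its change from a baseline it does not have, and no analysis estimates the minimal important difference it is collected for

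*Combined protocol and SAP*

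**What the plan says.** The Global Symptom Evaluation paragraph in C.7.2.1 gives the purpose: "This instrument is to estimate the minimal important difference in symptoms before treatment and after treatment". Patients first answer worse, about the same or better, and then grade the change. The improvement grades run "almost the same, hardly any better at all, a little better, somewhat better, moderately better, a good deal better" and go on to two stronger grades. The worsening grades run "almost the same, hardly worse, a good deal worse, a great deal worse, a very great deal worse, somewhat worse, moderately worse" and then repeat the three strongest, so the second half of the list reads "somewhat worse, moderately worse, a good deal worse, a great deal worse, a very great deal worse".

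On timing, the same paragraph says: "This evaluation will be performed on day 29 and day 57". Table 3 agrees, with marks at those two visits and none at baseline. The note under Table 3 allows the GSE to be completed by telephone.

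C.9 uses the GSE in two places:

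- **Pilot Analysis** plans "exploratory analyses on the changes in FACIT-F subscale (primary outcome measure) from baseline to Day 29 and baseline to Day 57". It then applies a similar analysis to a list of secondary outcomes that includes "SDMT, six- minute walk test, Borg Scale, GSE and Hand Grip Strength and Endurance Test", using paired t-tests or Wilcoxon tests. It also promises summaries of the secondary outcomes at each time point.
- **Secondary Analyses** gives a summary of the GSE by group and a chi-square comparison of its distribution between groups.

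Separately, C.9 fixes the clinical-benefit rule: "Response would be considered clinical beneficial if they improve 3.5 points on the FACIT- F fatigue subscale".

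**The concern.** There are three faults in the text as written.

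- **The response list.** A worsening patient is offered no *a little worse*, while an improving patient is offered *a little better*. Three worsening grades each appear at two positions. If answers are coded by position, or read out by telephone in the printed order, the same answer can receive two codes.
- **The pilot test.** A paired change from baseline needs a baseline value. The GSE has none, and none would have meaning, because the question already asks for change since starting treatment.
- **The purpose.** Estimating a minimal important difference means relating the patient's global rating to change on a score. Neither use of the GSE in C.9 does this.

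At stake are the usefulness of an exploratory instrument and a chance to set the clinical-benefit threshold beside data from this mixed-tumour population. C.9's efficacy test and sample size are not at stake.

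**Working it through.** **1. Counting the grades** (C.7.2.1, Global Symptom Evaluation)

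| Position | Better list | Worse list as printed |
|---|---|---|
| 1 | almost the same | almost the same |
| 2 | hardly any | hardly |
| 3 | a little | a good deal |
| 4 | somewhat | a great deal |
| 5 | moderately | a very great deal |
| 6 | a good deal | somewhat |
| 7 | a great deal | moderately |
| 8 | a very great deal | a good deal (repeat) |
| 9 | none | a great deal (repeat) |
| 10 | none | a very great deal (repeat) |

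The better list has 8 entries, all distinct and in rising order. The worse list has 10 entries, of which 10 − 3 = 7 are distinct. *Somewhat* and *moderately* come after the first printing of the strongest grade. Of the 8 improvement grades, 1 has no counterpart (*a little*).

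**2. Effect on the chi-square test.** With duplicates merged there are 8 + 1 + 7 = 16 possible answers. With 50 evaluable patients per arm (C.9, Power Considerations), that averages 50/16 = 3.1 patients per cell. Counting the duplicates separately gives 8 + 1 + 10 = 19 answers and 50/19 = 2.6 per cell. This matters only if the graded answers are tested. If only worse, same and better are compared, the duplicates have no effect. C.9 does not say which is meant.

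**3. Baseline against assessment times.** The pilot change analysis runs from baseline to Day 29 and from baseline to Day 57. GSE assessments take place on Days 29 and 57. There is no baseline value to pair with either.

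**4. Analyses that estimate a minimal important difference.** The GSE uses in C.9 are the pilot change test, the pilot summary, the by-group summary and the chi-square test. None relates a GSE grade to a change in FACIT-F or any other score, so the count is 0.

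**5. What an added table could show.** The plan expects 20% dropout from 128, leaving 0.8 × 128 ≈ 102 completers. Assume that 15 to 25 of them report a small improvement; the documents give no figure. The 95% half-width for mean FACIT-F change is 1.96 × SD/√n, with the two SDs from Power Considerations:

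| SD | n = 15 | n = 25 |
|---|---|---|
| 5.8 | 1.96 × 5.8/√15 = 2.9 | 1.96 × 5.8/√25 = 2.3 |
| 8.8 | 1.96 × 8.8/√15 = 4.5 | 1.96 × 8.8/√25 = 3.4 |

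Tabulating every grade separately would be too thin. If 102 patients spread evenly over 17 corrected answers (8 + 1 + 8; assumption), each has 102/17 = 6, and 1.96 × 5.8/√6 = 4.6 points.

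**The case against.** The case on the other side has real force, and it limits the point in five ways.

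- **The list can be rescued.** The repeated labels are identical and can be merged, and the wording of the seven distinct grades gives a natural order. The improvement side is intact, so a minimal improvement could still be estimated. A reader might infer that the worsening scale cannot be ordered, or that the GSE cannot serve its purpose at all. The text does not support either. What stands is the missing small-worsening grade and the risk of double coding.
- **The patient form has not been seen.** It is not in the supplied text and may carry the correct list. The error is shown for the protocol text only.
- **The pilot wording is loose.** With its grades scored, the GSE could be tested as a one-sample change against *about the same*, and the pilot summaries by time point remain usable. What stands is that the analysis described, change from baseline, does not fit this instrument.
- **The 3.5-point rule is not unsupported.** Power Considerations cites a 3 to 5 point range for clinically important differences and an exercise trial powered for 3.5. A reader might infer that the threshold is arbitrary or that the trial had to validate it. Neither follows, since a prespecified published cut-off is acceptable.
- **The link to FACIT-F is a suggestion.** The GSE asks about symptoms in general and not about fatigue, and A.2 lists it only among the exploratory measures. This is why the table should report the correlation between the two and be read as supportive.

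**Conclusion.** The point holds as three text-level faults in an exploratory outcome: a worsening list with 10 entries, 7 distinct grades and one grade missing; a pilot change-from-baseline analysis for a measure with no baseline; and a stated purpose that no planned analysis serves. Severity is low. The primary FACIT-F analysis, the sample size and the interim boundaries do not use the GSE.

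The precision figures rest on an assumed 15 to 25 patients in the small-improvement category, on the normal quantile, and on the plan's overall SDs holding within that category. At SD 8.8 the half-width (4.5 to 3.4 points) is about as large as the 3.5-point threshold itself. The added table would give context for planning the larger trial foreseen in the Future Studies section. It would not be a test of the threshold.

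**What to change.** 1. **C.7.2.1:** print the worsening list as the mirror of the improvement list, putting *worse* for *better* in each of the eight grades in the same order. Confirm that the patient form matches. If any forms were completed on the list as printed, merge the duplicated grades before analysis.
2. **C.9, Pilot Analysis:** take the GSE out of the list for paired change analysis. Report instead the proportion answering better at Day 29, among patients with a Day 29 GSE, with an exact 95% confidence interval.
3. **C.9, Secondary Analyses:** say whether the chi-square test uses the three broad answers or the grades. Add one descriptive table of mean baseline-to-Day-29 FACIT-F change by collapsed GSE category (worse, about the same, small improvement, larger improvement), arms pooled, with 95% confidence intervals and the GSE/FACIT-F correlation. State in advance which grades form each category, and label the table as supportive beside the 3.5-point rule.

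The cost is one corrected list, a check of the form, short rewording in C.9 and one table. No new visits, patients or data are needed.
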